4.2.3.3 Analysis of primary variable

The MMRM analysis of the primary endpoint in the Evaluable population will be considered the primary analysis.

The primary efficacy analysis will compare treatment groups (EQW vs. PBO) with respect to change in HbA1c from baseline (Visit 2 [Week 0]) to Visit 7 (Week 24) by using the MMRM approach. The model will include change in HbA1c as the dependent variable and treatment group, visit, interaction between visit and treatment, region, baseline HbA1c and interaction between visit and baseline HbA1c as the fixed effects. The variance - covariance structure to be used for this modelling will be unstructured (UN); if the model does not converge with unstructured variance – covariance matrix, then autoregressive order 1 (AR [1]) and heterogeneous autoregressive order 1 (ARH [1]) structures will be tried and the covariance structure will be decided based on model convergence status and the Akaike information criterion. The restricted maximum likelihood (REML) method will be used for parameter estimation, and the Kenward-Roget adjustment will be applied (ddfm=KR option in SAS PROC MIXED model statement. The least squares (LS) mean, 2-sided 95% confidence interval, and p-value of the difference in the change of HbA1c between the EQW and PBO groups at Visit 7 (Week 24) will be provided. The mean (SD) observed HbA1c at baseline and Week 24 will also be given by treatment group.

HbA1c data from post-baseline visits (including Early Termination) will be included in the MMRM analysis. See Section 4.1.3 for details on missing data handling.

For patients who initiate rescue medication or discontinue IP and continue study participation, only data before initiation of rescue medication or up to and including date of discontinuation from IP will be included in the MMRM analysis. If there is evidence that a measurement was taken prior to initiation of rescue medication, then this data will be included. If the measurement was taken on the date of initiation of rescue medication but time information is not available, then the measurement will be included. Namely, the data after initiation of rescue medication or after premature IP discontinuation will be excluded from the primary analysis.

Summaries and descriptive analysis of the primary endpoint will be performed using the Evaluable analysis set.

Subgroup analyses of primary endpoint

The primary endpoint, change from baseline in HbA1c at week 24, will be summarized descriptively for subgroups of interest listed below. Observed and change from baseline in HbA1c by visit will be presented. No statistical analyses will be conducted.

- HbA1c baseline strata (<9.0% or ≥9.0%)
- Age group: <10, 10 to 17, and >17.
- Country
- Region (North America (USA), South America (Mexico), Europe (Israel, Hungary, Bulgaria, Ukraine), Middle East (Kuwait))
- Sex –Male/Female
- Race
- Baseline BMI Percentile <3, 3-<85, 85-<97, ≥97

BMI percentile will be calculated using height and weight data collected on the CRF. The SAS macro from CDC website listed below will be used to calculate BMI percentile and the method provided on the website will be followed for analysis.

<https://www.cdc.gov/nccdphp/dnpao/growthcharts/resources/sas.htm>.

4.2.3.4 Sensitivity and supplementary analyses for primary endpoint

To further support the primary endpoint analysis and to examine the influence of missing data due to drop-out and/or receiving rescue therapy, sensitivity and supplementary estimands described in Section 4.2.3.1 are defined and will be addressed using an MMRM analysis at Week 24.

The MMRM model that will be used for analyzing the change in HbA1c will include treatment group, visit, interaction between visit and treatment, region, baseline HbA1c and interaction between visit and baseline HbA1c as the fixed effects. The variance - covariance structure to be used for this modelling will be the same as used for the primary analysis. The LS mean in each treatment group at Week 24, the standard error (SE), and the corresponding 95% CI, as well as the LS mean difference between treatment groups, the SE, the 95% CI, and

the p-value, will all be derived and presented from the MMRM model. The mean (SD) observed HbA1c at baseline and Week 24 will also be given by treatment group.

In addition, an imputation sensitivity analysis will test the assumption of MAR that is made by the MMRM analysis. For this purpose, a model that assumes missing not at random (MNAR) will be used, whereby assumptions for the missing data “stress test” the MAR assumptions of the primary analysis, by positing outcomes that, while clinically plausible, are likely to be worse for the EQW group than the outcomes assumed by MAR. A plausible stress test could assume that the outcome for the EQW treatment is somewhat worse than would be predicted by MMRM from the study data. Such a stress test would appropriately disadvantage the estimate of treatment effect, compared to the estimate of the primary analysis. In this way the MAR assumption of the primary analysis could be stress tested.

The proposed MNAR sensitivity analysis assumes that the trajectory after the intercurrent event from the EQW group, regardless of the type of event, can be modelled by that of PBO patients. This assumption will tend to result in smaller estimates of difference between the treatment groups, compared to those under the MAR assumption, and as such constitutes a reasonable stress test of the MAR assumption. Note that this approach constitutes a pattern mixture model as defined by Molenberghs and Kenward⁴. The patterns here are defined by the time of the intercurrent event, with the imputed values for both treatment groups modeled by observed outcomes from the placebo group only. Specifically, for a patient with missing/excluded observations after visit t , imputed value for the change from baseline at visit $t+n$ will be based on a model estimated from all in the control group who have an outcome observed at visit $t+n$ conditioning on that patient’s outcomes up to and including visit t . Then, the overall estimate of treatment effect is obtained by using Rubin’s rules to combine the imputed outcomes. Note that in this analysis, PBO missing/excluded observations are imputed assuming MAR and here follows the pattern of observed PBO observations, while missing/excluded observations for the EQW group are assumed MNAR. This strategy for imputation is commonly referred to as the Copy-Reference approach.

In summary, the pattern mixture models will be implemented by multiple imputation via the following steps;

Step 1: Non-monotone missing data (usually relatively infrequent) will be imputed using the MCMC statement of SAS PROC MI under the MAR assumption. The following variables will be included in the imputation model: treatment, region and HbA1c measurements from baseline to Week 24. Note: Dummy variables will be used for treatment and region. This will create a monotone missing pattern in the dataset within each treatment group. This step will create 1000 imputed datasets.

Step 2: Then the values for each pattern will be imputed via the sequential regression method, using SAS PROC MI statement MONOTONE REG. The imputation model will be estimated from the observed data in the PBO group and it will be used to impute missing/excluded observations in both treatment groups using the MNAR statement of SAS PROC MI. The following variables will be included in the imputation model: region and HbA1c measurements from baseline to Week 24.

Step 3: The imputed data from Step 1 and Step 2, along with observed data will be analyzed using the same MMRM model for the outcome of week 24 change from baseline as for the primary analysis. The estimates from multiple imputed datasets will be combined using Rubin's combination rules for statistical inference⁵ (using PROC MI ANALYZE).

The seed used will be 88281 for both steps 1 and 2.

4.2.3.5 Analysis of secondary variables

Summary statistics and frequency tables will be provided for all secondary endpoints by visit and treatment for the ITT analysis set during the controlled assessment period and separately for the subset of ITT patients who received open-label EQW during the extension period for the Treatment period (see Section 3.6.5 for Treatment period definition), unless otherwise stated.

Similar to the primary analysis, data including the Early Termination visit where applicable will be included in the MMRM and CMH analysis for secondary analysis variables. Data collected from an Early Termination visit will be mapped to the next closest scheduled visit. For patients who initiate rescue medication and continue study participation, data collected after the initiation of rescue medication will be excluded from analyses. Data collected after discontinuation of IP will be excluded from analyses for all secondary efficacy endpoints.

Change in HbA1c from baseline Visit 2 (Week 0) to Visit 10 (Week 52), and to each intermediate visit as applicable

The MMRM method for change in HbA1c will be used until Week 24 and to each intermediate visit, using the Evaluable analysis set, which is the same approach as stated in Section 4.2.3.3.

The least squares mean (LSM) change from baseline and SE bar by visit will be presented in a figure by treatment group. The p-value for the difference between treatment groups by visit will also be provided in the figure.

The observed values and change from baseline will be summarized by visit using descriptive statistics (mean, median, standard deviation, minimum, maximum). This will be provided separately for both the Evaluable analysis set during the controlled assessment period and for the subset of Evaluable patients who received open-label EQW during the extension period analysis set for the Treatment period.

HbA1c measures will be listed.

Change in fasting plasma glucose concentration, body weight, fasting insulin, lipids, blood pressure from baseline Visit 2 (Week 0) to Visit 7 (Week 24), Visit 10 (Week 52), and to each intermediate visit as applicable

The same MMRM approach will be used to analyze the change in body weight, blood pressure, fasting plasma glucose, and fasting insulin from baseline (Week 0) to Week 24, and each intermediate visit.

The least squares mean (LSM) change from baseline and SE bar by visit will be presented in a figure by treatment group. The p-value for the difference between treatment groups by visit will also be provided in the figure.

The observed values and change from baseline will be summarized by visit using descriptive statistics (mean, median, standard deviation, minimum, maximum) for body weight, blood pressure, fasting plasma glucose, fasting insulin and lipids. This will be provided separately for both the ITT analysis set during the controlled assessment period and for the subset of ITT patients who received open-label EQW during the extension period for the Treatment period.

The models for changes in body weight, blood pressure, fasting plasma glucose, and fasting insulin will include treatment group, visit, interaction between visit and treatment, region, baseline of the dependent variable, interaction between visit and baseline of the dependent variable and screening HbA1c strata ($<9.0\%$, $\geq 9.0\%$) as the fixed effects. The REML method will be used for parameter estimation. The least squares mean, 2-sided 95% confidence interval, and p-value of the difference in the endpoints of interests between the EQW and PBO groups will be provided.

FPG, body weight, fasting insulin, lipids and blood pressure (systolic and diastolic) will be presented in listings.

Proportions of patients achieving HbA1c goals at Visit 7 (Week 24), Visit 10 (Week 52), and at each intermediate visit

Proportions of patients having HbA1c goals of $<6.5\%$, $\leq 6.5\%$ and $<7.0\%$ at Week 24 and at each intermediate visit will be compared between treatments using the Evaluable analysis set via the CMH procedure, in which screening HbA1c strata ($<9.0\%$, $\geq 9.0\%$) will serve as the stratification factors.

A bar chart of the percentage of patients achieving HbA1c goals of $<6.5\%$, $\leq 6.5\%$ and $<7.0\%$ by visit and treatment group will be provided along with p-values.

Any Evaluable patient without HbA1c value at the endpoint will be considered as not achieving HbA1c goal at endpoint. The denominator will be the total number of Evaluable patients in a treatment group, and the numerator will be the number of patients achieving HbA1c $<6.5\%$, $\leq 6.5\%$ and $<7.0\%$.

As a sensitivity analysis also in the Evaluable analysis set, the probabilities of patients reaching HbA1c targets of $<6.5\%$, $\leq 6.5\%$ and $<7.0\%$ will be analyzed to Week 24 using the CMH procedure, with missing data imputed using MI pattern mixture model imputation. HbA1c strata ($<9.0\%$, $\geq 9.0\%$) will serve as the stratification factors. The imputed HbA1c data for the sensitivity analysis of the primary endpoint (Section 4.2.3.4) will be used for this analysis.

The number and percentage of patients having HbA1c target values of $<6.5\%$, $\leq 6.5\%$ and $<7.0\%$ will be summarized by visit and treatment group. This will be provided separately for both the Evaluable analysis set during the controlled assessment period and for the subset of Evaluable patients who received open-label EQW during the extension period for the Treatment period.

Proportions of patients discontinuing the study, needing rescue due to failure to maintain glycemic control, and number of rescue episodes at Visit 7 (Week 24), Visit 10 (Week 52), and at each intermediate visit

A Kaplan-Meier table and corresponding figure of time to rescue will be provided. Patients who are not rescued will be censored at Week 24 visit or last dose of study medication for those who discontinue study treatment for reasons unrelated to lack of glycemic control, as indicated by an adverse event withdrawal that required rescue medication prior to Week 24 visit.

The number and percentage of patients needing rescue due to failure to maintain glycemic control will be summarized by visit according to the windows defined in Section 4.3.1. This will be provided separately for both the ITT analysis set during the controlled assessment period and for the subset of ITT patients who received open-label EQW during the extension period for the Treatment period. The number of patients included at each analysis visit will be derived by including patients in the counts at every visit up to study completion date or date of last dose of study medication for patients who prematurely discontinue study medication.

Data collected after study treatment discontinuation will be excluded from summaries.

The proportion of patients discontinuing the study will be presented in the disposition table, by study period.

Change in beta-cell function (HOMA-B) and insulin sensitivity (HOMA-S) as measured by homeostasis model assessments in patients not taking insulin from baseline Visit 2 (Week 0) to Visit 7 (Week 24), Visit 10 (Week 52), and to each intermediate visit as applicable

The same MMRM approach will be used to analyze the change in beta-cell function (HOMA-B) and insulin sensitivity (HOMA-S) as measured by homeostasis model assessments in patients not taking insulin from baseline Visit 2 (Week 0) to Week 24, and each intermediate visit.

The least squares mean (LSM) change from baseline and SE bar by visit will be presented in a figure by treatment group. The p-value for the difference between treatment groups by visit will also be provided in the figure.

The observed values and change from baseline for these parameters will be summarized by visit using descriptive statistics (mean, median, standard deviation, minimum, maximum). This will be provided separately for both the ITT analysis set during the controlled assessment period and for the subset of ITT patients who received open-label EQW during the extension period for the Treatment period.

The effects of the study medications on HOMA will be examined. The pancreatic beta-cell function (HOMA-B) and peripheral and hepatic insulin sensitivity (HOMA-S) will be computed from a computerized HOMA model, which can predict the plasma glucose, insulin, c-peptide, and proinsulin concentrations for any possible combination of these 2 parameters in the fasting state in patients not taking insulin.

HOMA-B and HOMA-S will be computed from a computerized HOMA model, the HOMA Calculator². The HOMA Calculator, developed by Diabetes Trials Unit at the Oxford Center for Diabetes, Endocrinology, and Metabolism, is a computer algorithm that takes account of variations in hepatic and peripheral glucose resistance, increases in the insulin secretion curve for plasma glucose concentrations above 10 mmol/L (180 mg/dL), and the contribution of circulating proinsulin (e.g., C-peptide) to estimate the steady state beta-cell function and insulin sensitivity, as percentages of a normal reference population. The model assumes %HOMA-B and %HOMA-S values of 100% in normal young adults as a recalibration.

All HOMA parameters will be analyzed on a logarithmic scale (natural logarithmic transformation), and then back-transformed to the original scale for result presentation using the following formulae:

Geometric Mean = $\exp(\text{mean}(\log(X)))$

SE of Geometric Mean = Geometric Mean * SE of Mean (log (X))

LS means will be back-transformed in the same way.

Separate tables of back-transformed and non-transformed results will be provided.

Homeostasis results will be listed.

Plasma exenatide concentrations at baseline Visit 2 (Week 0), Visit 7 (Week 24), Visit 10 (Week 52), and each intermediate visit, as applicable.

Descriptive statistics (geometric mean, geometric coefficient of variation: GCV %, geometric standard deviation factor: GSD, arithmetic mean, standard deviation, coefficient of variation: CV %, median, minimum, maximum) will be presented by visit and controlled assessment period treatment group for the PK analysis set.

The geometric mean plasma exenatide concentration with GSD bars will be plotted over time by treatment group.

Plasma exenatide concentrations will be listed.

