2.2 Secondary objectives

The secondary objectives of this study are:

- To compare the effects of EQW following 24 weeks of treatment to those achieved by placebo in children and adolescents with type 2 diabetes mellitus on the following:
 - Fasting plasma glucose concentration
 - Proportion of patients achieving HbA1c goals
 - Body weight and Tanner pubertal stage
 - Blood pressure and lipids
- To assess the effects of long-term exenatide once weekly therapy (~1 year) in children and adolescents with type 2 diabetes mellitus on the following:
 - Long-term safety and tolerability
 - Parameters related to glycemic control, including HbA1c, fasting plasma glucose concentration, and proportion of patients achieving HbA1c goals

- Body weight and Tanner pubertal stage
- Blood pressure and lipids
- To examine the effect of exenatide once weekly on beta-cell function (HOMA-B) and insulin sensitivity (HOMA-S) as measured by the homeostatic model assessment (HOMA) in children and adolescents with type 2 diabetes who are not taking insulin
- To assess the pharmacokinetics of exenatide once weekly in children and adolescents with type 2 diabetes

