4.2 Inclusion criteria

For inclusion in the study patients should fulfil the following criteria:

1. Is a child or an adolescent of 10 to <18 years old, at Visit 1 (Screening)
2. Has been diagnosed with type 2 diabetes mellitus per American Diabetes Association diagnostic criteria
3. HbA1c of 6.5% to 11.0%, inclusive, in patients not taking insulin/SU, and of 6.5% to 12.0%, inclusive, in patients taking insulin/SU, at Visit 1 (Screening)
4. Has a C-peptide of >0.6 ng/mL at Visit 1 (Screening)
5. Has been treated with diet and exercise alone or in combination with a stable dose of an oral antidiabetic agent (eg, metformin and/or SU) and/or insulin for their type 2 diabetes for at least 2 months prior to Visit 1 (Screening)
6. Has a fasting plasma glucose concentration <280 mg/dL (15.5 mmol/L) at Visit 1 (Screening)
7. Either is not treated with or has been on a stable treatment regimen with any of the following medications for a minimum of 1 month prior to Visit 1 (Screening):
 - (a) Oral contraceptives (female patients)
 - (b) Antihypertensive agents
 - (c) Lipid-lowering agents
 - (d) Thyroid replacement therapy
 - (e) Antidepressant agents
8. Is male, or is female and meets all the following criteria:
 - (a) Not breastfeeding
 - (b) Negative serum pregnancy test result (human chorionic gonadotropin, beta subunit [β hCG]) at Visit 1 (Screening)
 - (c) If of childbearing potential, must practice and be willing to continue to practice appropriate birth control (defined as at least 1 method which results in a low failure rate, ie, less than 1% per year, when used consistently and correctly, such as implants, injectables, hormonal contraceptives, some intrauterine contraceptive

- devices, sexual abstinence, tubal ligation or occlusion, or a vasectomized partner) during the entire duration of the study and must not be planning to conceive
9. Has clinical laboratory test values (clinical chemistry, hematology, and urinalysis) judged as not clinically significant by the Investigator at Visit 1 (Screening)
 10. Has physical examination and ECG results deemed not clinically significant by the Investigator at Visit 2 (Week 0)

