3.2 Secondary efficacy variables

The following are the secondary efficacy endpoints:

- Change in HbA1c from baseline Visit 2 (Week 0) to Visit 10 (Week 52), and to each intermediate visit as applicable
- Change in fasting plasma glucose concentration from baseline Visit 2 (Week 0) to Visit 7 (Week 24), Visit 10 (Week 52), and to each intermediate visit as applicable
- Proportions of patients achieving HbA1c goals of <6.5%, ≤6.5% and <7.0% at Visit 7 (Week 24), Visit 10 (Week 52), and at each intermediate visit as applicable
- Change in body weight from baseline Visit 2 (Week 0) to Visit 7 (Week 24), Visit 10 (Week 52), and to each intermediate visit as applicable

- Change in fasting insulin from baseline Visit 2 (Week 0) to Visit 7 (Week 24), Visit 10 (Week 52), and to each intermediate visit as applicable
- Change in beta-cell function (HOMA-B) and insulin sensitivity (HOMA-S) as measured by homeostasis model assessments in EQW patients not taking insulin from baseline Visit 2 (Week 0) to Visit 7 (Week 24), Visit 10 (Week 52), and to each intermediate visit as applicable
- Change in lipids (total cholesterol, high-density lipoprotein [HDL], low-density lipoprotein [LDL] and triglycerides) from baseline Visit 2 (Week 0) to Visit 5 (Week 12), Visit 7 (Week 24), Visit 10 (Week 52), and to each intermediate visit as applicable
- Change in blood pressure (systolic and diastolic) from baseline Visit 2 (Week 0) to Visit 7 (Week 24), Visit 10 (Week 52), and to each intermediate visit as applicable
- Plasma exenatide concentrations at baseline Visit 2 (Week 0), Visit 7 (Week 24), Visit 10 (Week 52), and each intermediate visit, as applicable
- Proportions of patients discontinuing the study and the proportion of patients needing rescue due to failure to maintain glycemic control, and number of rescue episodes at Visit 7 (Week 24), Visit 10 (Week 52), and at each intermediate visit as applicable

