CSP Section 12.6.1 states that last observation carried forward will be used for missing data at endpoint for proportion of patients meeting HbA1c goals of $\leq 6.5\%$ and $< 7.0\%$, however, patients with missing HbA1c at endpoint will be considered as non-responders. Additionally, the logistic regression sensitivity analysis described in the CSP has been replaced with a more appropriate CMH analysis using MI pattern mixture model imputation (Sections 4.2.3.4 and 4.2.3.5), as this tests the robustness of the results from the main analysis by altering the missing data assumption.

CSP Section 12.6.1 stipulates ‘The analyses of all other efficacy endpoints will be performed in ITT population.’ Upon review of the endpoints it was agreed that all endpoints related to HbA1c should be evaluated using the Evaluable analysis set.

CSP Section 12.6.1 outlines a MMRM method will be implemented for the secondary efficacy endpoint, lipids. It was agreed after blinded data review that the data could be sufficiently reviewed as summary statistics.

CSP Section 12.6.2 specifies that both baseline HbA1c and HbA1c strata will be included in the MMRM model for the primary analysis. However, these variables will be highly correlated resulting in multicollinearity in the statistical model. Therefore, HbA1c strata will not be included in the primary model. For secondary and exploratory MMRM analyses, screening HbA1c strata will be used in the model instead of continuous baseline HbA1c.

The sensitivity and supportive analyses in Section 4.2.3.4 were not specified in the CSP and have been added to further support the primary analysis and to examine the influence of missing data due to drop-out and/or receiving rescue therapy.

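### Patients can enter with HbA1c already below 7.0%, and no analysis of the <7.0% goal accounts for who was at goal at baseline (minor)

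*SAP*

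**What the plan says.** - **Entry.** Protocol section 4.2, criterion 3, requires "HbA1c of 6.5% to 11.0%, inclusive, in patients not taking insulin/SU, and of 6.5% to 12.0%, inclusive, in patients taking insulin/SU" at screening.
- **Objective and endpoint.** Protocol section 2.2 lists "Proportion of patients achieving HbA1c goals" among the Week 24 comparisons with placebo. SAP section 3.2 sets three goals: <6.5%, ≤6.5% and <7.0%.
- **Scoring.** SAP section 4.2.3.5: "The denominator will be the total number of Evaluable patients in a treatment group", and "the numerator will be the number of patients achieving HbA1c" below the threshold. Baseline HbA1c plays no part in either count.
- **Test.** In the same section, the goal proportions "will be compared between treatments using the Evaluable analysis set via the CMH procedure, in which screening HbA1c strata" are the stratification factors. There are two strata, below 9.0% and 9.0% or above. The sensitivity analysis repeats this test on imputed data with the same strata.
- **Dropped analysis.** Protocol section 12.6.3 planned a supportive logistic regression with baseline HbA1c as a continuous covariate. SAP section 5 states that "the logistic regression sensitivity analysis described in the CSP has been replaced with a more appropriate CMH analysis using MI pattern mixture model imputation". The reason given there is that the replacement varies the missing-data assumption; the loss of baseline adjustment is not discussed.
- **Other displays.** SAP Table 1 summarizes baseline HbA1c as a continuous variable and by the 9.0% cut. The subgroup summaries in section 4.2.3.3 cover the primary endpoint only and use the same cut. HbA1c values are also listed.

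**The concern.** The lower stratum puts patients who start at goal (6.5% to 6.9%) together with patients who start as high as 8.9%. The two groups have very different chances of being below 7.0% at Week 24. The first has only to stay where it is; the second has to improve.

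Two things are at stake. The first is meaning: the percentages, the bar chart and the p-values will be read as the share of patients brought to goal, when part of that share was there on Day 1. The second is stability: with about 20 placebo patients, a chance difference between arms in the number at goal at entry feeds into the comparison, and neither goal analysis would remove it. No planned table shows that number, so a reader would have to count it from listings.

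**Working it through.** **The plan's own figure.** The documents give no power or assumed rate for the goal endpoint. The stated 74% is for the primary endpoint. A two-sample t-test with 50 versus 20 patients, difference 0.7, SD 1.0 and two-sided 0.05 gives 74.2%, so it reproduces. It does not bear on this point, but it supplies the design effect used in step 4.

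**Inputs from the documents.** Entry from 6.5%; strata cut at 9.0%; 5:2 allocation; at least 50 and 20 evaluable patients, or 55 and 22 if all 77 randomized patients are counted; effect −0.7%, SD 1.0%.

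**Inputs assumed.** The documents do not give the share q already below 7.0% at entry; 10% to 30% is shown. Assumed Week 24 rates of HbA1c <7.0%, EQW versus placebo: 80% vs 60% if at goal at entry, 45% vs 12% at 7.0% to 8.9%, and 15% vs 3% at 9.0% or above. The last group is assumed to be 35% of patients.

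**1. Who the placebo achievers are.** Share at goal at entry = 0.60q / [0.60q + 0.12(0.65 − q) + 0.03 × 0.35].
- q = 10%: 0.060 / 0.1365 = 44%
- q = 20%: 0.120 / 0.1845 = 65%
- q = 30%: 0.180 / 0.2325 = 77%

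At q = 20% the placebo rate is 18% overall, but (0.054 + 0.0105) / 0.80 = 8% among those above goal at entry.

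**2. Effect of a few patients.** Replacing a placebo patient at 7.0% to 8.9% with one already at goal adds 0.60 − 0.12 = 0.48 expected achievers. Among 22 patients:
- two such patients: 2 × 0.48 / 22 = 4.4 points
- three such patients: 3 × 0.48 / 22 = 6.5 points

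**3. How likely an imbalance is.** By exact binomial calculation with 50 versus 20 patients, the chance that the arms differ by 10 points or more in the at-goal share is 10%, 23%, 31% and 37% for true shares of 5%, 10%, 15% and 20%.

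**4. Planned test against one with an added cut at 7.0%, at the design effect.** This used 6,000 simulated trials per scenario, 50 versus 20 patients, normal baseline with mean 7.5 to 8.5 and SD 1.3 truncated to 6.5–11.0, and change SD 1.0. Between 7% and 17% of patients then start below 7.0%.

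| Quantity | Cut at 9.0% only | Cuts at 7.0% and 9.0% |
|---|---|---|
| Type I error | 0.044–0.051 | 0.044–0.049 |
| Mean risk difference | 0.139–0.190 | 0.138–0.189 |
| Shift in risk difference per 10-point imbalance | about 4 points | about 0 |
| Power | 0.25–0.34 | 0.25–0.36 |

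Scenario by scenario, the power gain is about 1 to 2 points.

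**5. The same comparison under the assumed rates.** With 55 versus 22 patients and 60,000 simulated trials, power rises from 62% to 66%, 55% to 60% and 50% to 55% at q = 10%, 20% and 30%. These rates imply a risk difference of 0.22 to 0.24, larger than the design effect gives, so these gains of 4 to 5 points are the upper end.

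**6. Empty strata.** A stratum with no placebo patients contributes nothing to the CMH test. With 22 placebo patients this has probability 0.90^22 = 10% at a 10% at-goal share and 0.95^22 = 32% at a 5% share.

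**The case against.** The endpoint is a state at a visit. Parts of the SAP speak of patients having a goal value at Week 24, and counting those patients over all Evaluable patients answers that question correctly. Restricting to patients above goal at entry answers a different one. This stands, and it is why the planned analysis should be kept and not replaced.

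At-goal patients are randomized to both arms. A reader might infer that the comparison is biased or its error rate inflated. The documents do not support that: step 4 shows the same mean difference and nominal type I error with either stratification.

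A reader might also infer that HbA1c is not adjusted for at all, or that two or three patients could move the placebo rate by 10 points. Neither is right. The 9.0% cut adjusts coarsely, and what is missing is at-goal status. The 10-point figure would require every at-goal patient to be a certain achiever and every other patient a certain non-achiever.

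The goal tests are outside the four-step hierarchy in SAP section 4.2.3.2, so their p-values are exploratory. The primary model adjusts for continuous baseline HbA1c. Dropping the logistic model was declared. All this limits the weight of the point, but none of it shows who was at goal at entry or brings that into a goal analysis. Baseline HbA1c does enter the imputation model for the sensitivity analysis, but the comparison made afterwards still uses only the 9.0% cut.

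**Conclusion.** The point holds as a minor one. For the <7.0% goal, neither planned analysis distinguishes reaching goal from staying there, and both are open to chance imbalance in at-goal status. The size is about 4 to 7 points on the placebo rate for two or three extra at-goal patients, and about 1 to 5 points of power. Both figures, and the 44% to 77% in step 1, rest on assumed rates and an assumed at-goal share. The direction does not: whenever patients who start at goal are likelier to finish below 7.0%, they raise the achieving rate in their arm.

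It would be wrong to extend this equally to all three goals. Nobody below 6.5% at screening is eligible, so the two 6.5% goals are touched only by patients at exactly 6.5% (for ≤6.5%) or by drift between screening and baseline, which may be up to 35 days apart with the lifestyle program already begun. The primary result is not affected.

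**What to change.** For the <7.0% goal, keep the planned CMH test and add to the SAP:

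1. One baseline-adjusted analysis: either a CMH test with baseline HbA1c strata <7.0%, 7.0% to <9.0% and ≥9.0%, or the protocol's logistic model with continuous baseline HbA1c.
2. The number and percentage of patients below 7.0% at baseline, by arm.
3. A table of the <7.0% goal in patients with baseline HbA1c of 7.0% or more.

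Use the baseline value, not the screening value, to define these groups.

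The cost is SAP wording, one extra analysis and one table, all from data already collected. The restricted table has fewer patients. In the three-stratum test, EQW patients in the <7.0% stratum drop out if no placebo patient falls there (step 6). The logistic model avoids this and may be the better choice if the at-goal share turns out low.
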